**REVISION HISTORY**

Revision #	Version Date	Summary of Changes	Consent Change?
1	17JAN2020	Added new method of recruitment (Interest Flyer)	No

PROTOCOL TITLE: Randomized, Controlled Trial of an Individualized Exercise Oncology Program for Newly Diagnosed Breast Cancer Patients

## 1.0 Study Summary

Study Title	Randomized, Controlled Trial of an Individualized Exercise Oncology Program for Newly Diagnosed Breast Cancer Patients
Study Design	Randomized, controlled trial
Primary Objective	The primary objective is to test the effect of an individualized exercise oncology program on healthcare utilization, 30-day hospital readmission, pain, and cancer treatment tolerance.
Secondary Objective(s)	The secondary objective is to examine the feasibility of an individualized exercise oncology program via adherence and attrition rates.
Research Intervention(s)/Investigational Agent(s)	Individualized Exercise Oncology Program
IND/IDE #	N/A
Study Population	Female patients age 18+ newly diagnosed with stage 0, 1 or 2 breast cancer.
Sample Size	70
Study Duration for individual participants	12 weeks
Study Specific Abbreviations/Definitions	N/A

## 2.0 Objectives\*

The primary objective is to test the effect of an individualized exercise oncology program on healthcare utilization, 30-day hospital readmission, pain, and cancer treatment tolerance.

H1: Among women newly diagnosed with stage 0, 1 or 2 breast cancer, those enrolled in an individualized exercise oncology program will have fewer emergency room (ER) visits, fewer hospital encounters, fewer 30-day hospital readmissions, fewer breaks in cancer treatment, less pain, and better cancer treatment tolerance than those in the control group over 3 months.

The secondary objective is to examine the feasibility of an individualized exercise oncology program via adherence and attrition rates.

H2: Among women newly diagnosed with stage 0, 1 or 2 breast cancer and enrolled in an individualized exercise oncology program, adherence to scheduled exercise sessions will average 70% or more, and program attrition will average 70% or less over 3 months.

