### Secondary Study Endpoints:

- Exercise session adherence rate among the Exercise Group, collected from the Maple Tree Cancer Alliance participant records.
- Exercise program attrition rate among the Exercise Group, collected from the Maple Tree Cancer Alliance participant records.

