## 5.0 Study Intervention/Investigational Agent

### Exercise Group

The study intervention is a supervised, individualized exercise oncology program described in previous literature and provided by Maple Tree Cancer Alliance, a non-profit organization providing exercise training to individuals with cancer (<https://www.mapletreecanceralliance.org/>). This organization was founded in 2011 and currently operates in 9 hospitals serving Ohio and Pennsylvania, offering free exercise programs and nutritional guidance to approximately 500 patients annually to help relieve side effects related to cancer treatment.

Patients in the supervised, individualized exercise oncology program (Exercise Group) will complete a 60-minute exercise session once per week for 12 weeks at Maple Tree Cancer Alliance. The exercise sessions will be individualized to the patient's needs and fitness level by a trainer with a bachelor's degree in exercise science and a national certification for exercise oncology. A patient will work with the same trainer throughout the study, who will plan the patient's individualized exercise regimen, and who will provide one-on-one supervision for the duration of each 60-minute session. Each 60-minute session will include cardiovascular, strength, and flexibility training.

Cardiovascular exercise will be performed on a treadmill. The intensity level for the aerobic exercise ranges from 30-45% of the individual's predicted VO2max, controlled by heart monitors (model S810i; Polar Electro) and lasting 30 min. Strength training will involve a full body workout, with emphasis on all major muscle groups and employing machines, free weights, and resistance tubing. Patients will complete 3 sets of 10 repetitions for each strength exercise. Flexibility training will involve static stretching of all major muscle groups for 15-20 seconds at the completion of each workout.

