## 12.0 Local Number of Subjects

A total of 70 subjects will be enrolled (35 in each study group). This sample size provides 80% power to detect a medium effect size in number of missed treatment fractions between study groups. Only subjects who meet eligibility criteria will be enrolled.

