## 14.0 Withdrawal of Subjects\*

Any study patient who experiences a safety endpoint under section 4.0, including recommendation to stop physical activity by treating oncologist, will be withdrawn from the study. Final, non-physical activity measures will be collected on patients who are withdrawn.

As Maple Tree provides free services to patients undergoing cancer treatment, a patient withdrawn from the study for safety reasons could, at a later date and when it is deemed safe by her physician, again receive exercise services at Maple Tree (outside the study context).

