### Data Analysis Plan:

Data will be analyzed using IBM SPSS Statistics version 25.0. Continuous variables will be described using mean, median, standard deviation, and range. Nominal variables will be described using frequency and percentage.

Baseline demographic and clinical characteristics will be compared between treatment and control groups to establish equivalence; any statistically significant differences between study groups will be controlled statistically. Continuous endpoints will be tested for normality using Shapiro-Wilk tests. Differences between study groups on continuous endpoints will be evaluated using independent samples *t*-tests for normally distributed endpoints and Mann-Whitney *U* tests for non-normally distributed endpoints. Nominal endpoints will be compared between groups using chi-square tests. Alpha will be set to .05, two-tailed for all tests.

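### H2 accepts program attrition of up to 70%, so the attrition half of the feasibility criterion is met with 24 of 35 exercise patients lost, and no justification is given

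*Combined protocol and SAP*

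**What the plan says.** H2 in Section 2.0 is the only success criterion stated for the only secondary objective, feasibility. It has two conditions: "adherence to scheduled exercise sessions will average 70% or more, and program attrition will average 70% or less over 3 months". No reason is given for either figure.

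Section 4.0 lists the matching endpoints and their source: "Exercise session adherence rate among the Exercise Group, collected from the Maple Tree Cancer Alliance participant records" and "Exercise program attrition rate among the Exercise Group, collected from the Maple Tree Cancer Alliance participant records". It gives no formula for either rate.

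The base can be read from other sections. Section 12.0 plans 35 patients per arm. Section 6.0 assigns patients to an arm at enrollment, before any session. Under Section 5.0, exercise patients "will complete a 60-minute exercise session once per week for 12 weeks". Section 14.0 says that a patient with a safety endpoint, "including recommendation to stop physical activity by treating oncologist, will be withdrawn from the study".

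The Data Analysis Plan in Section 17.0 covers description ("Continuous variables will be described using mean, median, standard deviation, and range") and between-group tests. It contains no rule specific to H2.

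**The concern.** A feasibility criterion should be able to fail when a program does not keep its patients. An attrition ceiling of 70% allows more than two thirds of the exercise arm to leave. A program that loses half its patients would almost always pass this half, so the feasibility verdict would rest nearly entirely on the adherence half.

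At stake is the claim that the program was shown to be feasible. A reader told that H2 was supported would take this to mean acceptable retention, and the attrition condition as written does not establish that.

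**Working it through.** **Inputs.** Exercise arm n = 35 (Section 12.0; Appendix A gives 5 exercise assignments in each of 7 blocks of 10, so 35). Scheduled sessions: 12 per patient (Section 5.0), so 35 × 12 = 420. Limits: attrition ≤ 70%, adherence ≥ 70% (Section 2.0). The documents give no expected attrition, dropout time or attendance; the values used for these below are assumptions. The 70% limit is stipulated, so there is no derivation to reproduce.

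**Step 1: attrition half alone.** 0.70 × 35 = 24.5. Hence 24/35 = 68.6% passes and 25/35 = 71.4% fails. The condition can be met with 11 patients left.

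**Step 2: how often that half is met.** With the number lost X ~ Binomial(35, p), the chance of meeting it is P(X ≤ 24):

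| Assumed true attrition p | P(condition met) |
|---|---|
| 40% | above 99.9% |
| 50% | 99% |
| 60% | 89% |
| 70% | 49% |

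**Step 3: both halves together.** Let k patients leave after m weekly sessions, let q be attendance while enrolled, and count sessions after dropout as missed. Then

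adherence = q × [12(35 − k) + m k] / 420.

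The largest k ≤ 24 with adherence of at least 70% is:

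| Sessions before dropout (m) | q = 100% | q = 95% | q = 90% |
|---|---|---|---|
| 0 | 10 | 9 | 7 |
| 3 | 14 | 12 | 10 |
| 6 | 21 | 18 | 15 |
| 9 | 24 | 24 | 24 |

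Checks at q = 100%:
- m = 0, k = 10: 300/420 = 71.4% passes; k = 11: 288/420 = 68.6% fails.
- m = 6, k = 21: (168 + 126)/420 = 70.0%, just passes.
- m = 9, k = 24: (132 + 216)/420 = 82.9%, so the attrition limit is what binds.

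**Step 4: when a majority can be lost.** A majority is k = 18. Adherence of 70% needs 0.70 × 420 = 294 sessions attended, so m ≥ (294/q − 12 × 17)/18. This gives 5.0, 5.9 and 6.8 sessions at q = 100%, 95% and 90%. If dropouts leave earlier than that on average, H2 fails before a majority is lost.

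**The case against.** The strongest reply is that H2 is a joint condition and the adherence half protects it. Much of this stands. When all 420 sessions are counted, heavy early dropout makes H2 fail, as Step 3 shows. The protection weakens as dropout comes later, and it does nothing to justify the attrition figure.

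A reader might go further and infer that the counting rules are wide open, so that H2 could be met with 11 patients left whenever they left. The documents do not support this. Adherence is to scheduled sessions over 3 months at one a week for 12 weeks, which points to 12 sessions per patient. Both rates are among the Exercise Group, formed by assignment at enrollment, so never-starters belong to the 35. A patient withdrawn from the study is, in plain reading, attrition. The sentence "Final, non-physical activity measures will be collected on patients who are withdrawn" concerns final data collection. Attendance comes from the program's own records, so the sentence does not take later sessions out of the denominator.

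What remains is that none of this is written as a definition, and a different choice would matter. Suppose 18 patients leave after 6 weeks with 90% attendance until then (assumed). Sessions attended are 0.90 × (12 × 17 + 6 × 18) = 0.90 × 312 = 280.8. Adherence is 280.8/420 = 66.9% on the natural reading and 280.8/312 = 90% if sessions after dropout are left out. H2 fails in the first case and is met in the second. That supports writing the natural reading down, but it does not show that the plan adopts the other one.

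A reader might also infer that 70% is a slip for 30%, since the two figures match. That is plausible but unconfirmed. A slip would still sit in the operative hypothesis and need correcting.

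**Conclusion.** The concern holds for the attrition limit. It is unjustified, is met with up to 24 of 35 lost, and would be met with probability 99% at an assumed true attrition of 50%. On the natural reading of the denominators, adherence is a real but partial guard. H2 can be met after a majority is lost only if those patients leave after about 5 to 7 sessions or later, on the assumed attendance of 90% to 100%.

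It would go too far to say that H2 as a whole tolerates 24 losses at any time, or that the rates have no base. The limit also does no harm to the trial's main comparison: H2 is not a stopping rule and does not enter the between-group tests. The effect is limited to the feasibility conclusion. The point is worth fixing because H2 is the only criterion for that conclusion and the correction is small.

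**What to change.** Before results are seen:

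1. In Section 2.0, replace the 70% attrition limit with one that tests feasibility, give the reason for it, and state it as a single proportion of the exercise arm. The sponsor sets the figure. If 70% retention was meant, the limit is attrition of 30% or less: 0.30 × 35 = 10.5, so 10/35 = 28.6% passes and 11/35 = 31.4% fails.
2. In Section 4.0, confirm the natural reading of both rates. The denominator is every patient randomised to exercise. Never-starters and Section 14.0 withdrawals count as attrition. Adherence is sessions attended out of 12, with sessions after dropout counted as missed. State one stop rule and apply it alike to patients who announce that they are leaving and to those who simply cease to attend.

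The cost is one sentence in Section 2.0 and two definitions in Section 4.0. The downside is that H2 becomes harder to meet. Under a 30% limit, P(X ≤ 10) is 93%, 51% and 11% at assumed true attrition of 20%, 30% and 40%. Counting Section 14.0 withdrawals against the program is a choice about how the rate is reported; it does not touch the withdrawal rule itself.

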## 3.0 Background\*

In 2018, it was estimated that there were 1.7 million new cancer diagnoses in the U.S. For all types of cancer, mortality rates are on the decline, and patients are living longer with the chronic and late effects of treatment. This often results in costly hospital readmissions and emergency department (ED) visits, leading to increased costs, lowered health outcomes, and lengthened stays for patients.

Several meta-analyses report that exercise interventions are beneficial for patients undergoing cancer treatment, in that they reduce symptom severity and improve cancer-related fatigue, cardiac function, muscle weakness, and overall quality of life. Yet, it still remains that less than 5% of patients are ever referred to an exercise oncology program during treatment. Therefore, economic evaluations of exercise oncology are warranted, in attempt to evaluate the integration of exercise oncology as a standard part of clinical practice.

Maple Tree Cancer Alliance has developed an oncology exercise program, which results in improved health outcomes, and also cost-saving for facilities and payers. Our retrospective data demonstrated that individualized exercise during cancer treatment significantly reduced ED visits, 30-day readmissions, and length of hospital stays resulting in a payer benefit of \$3,000/patient over the first 6 months of enrollment into the Maple Tree Exercise Oncology program^2. As a follow up to this research, the purpose of the present study is to prospectively analyze the cost savings of an individualized exercise oncology program when under a rigorous, randomized, controlled design. We hypothesize that

**PROTOCOL TITLE:** Randomized, Controlled Trial of an Individualized Exercise Oncology Program for Newly Diagnosed Breast Cancer Patients

individualized exercise training during cancer treatment will improve treatment outcome, lending to a decrease in healthcare-related expenditure.

## **4.0 Study Endpoints\***

### Primary Study Endpoints:

- Total number of missed fractions, determined via EMR
- A break in cancer treatment, defined as missing  $\geq 3$  fractions due to patient condition, determined via EMR
- ER visits, as determined via EMR
- Inpatient and outpatient hospital encounters, as determined via EMR
- Hospital readmission for the same presenting issue, as determined via EMR
- Hospital length of stay (if hospitalized), as determined via EMR
- Cancer treatment adherence, determined via EMR
- Medications for cancer treatment symptom management, determined via EMR
- Cancer treatment-related side effects, determined via EMR
- Patient-rated pain measured by visual analog scale, as determined via EMR
- Cancer treatment tolerance, measured by the Eastern Cooperative Oncology Group (ECOG) Performance Status score, as determined via EMR
- Quality of Life, as measured by the McGill Quality of Life Measure, administered in-person at weeks 1 and 12  
[\(http://www.npcrc.org/files/news/mcgill\\_quality\\_of\\_life.pdf\)](http://www.npcrc.org/files/news/mcgill_quality_of_life.pdf)

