## 15.0 Risks to Subjects\*

The risks associated with the study intervention are commensurate with light to moderate physical activity, such as muscle soreness. Given the low-impact nature of the exercise and the one-on-one supervision during exercise sessions, the risk of injury or another adverse outcome is very low. Participants in the Exercise Group will have an exercise program individualized to their needs and physical abilities, and participants will be closely monitored during exercise sessions. The

**PROTOCOL TITLE:** Randomized, Controlled Trial of an Individualized Exercise Oncology Program for Newly Diagnosed Breast Cancer Patients

study will not be blinded; patients and treating physicians will be aware of group status and if the treating oncologist recommends the subject stop physical activity, the subject will be withdrawn from the study.

The Exercise Group may incur some travel costs to attend exercise sessions.

No psychological, social, or legal risks are anticipated.

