## **17.0 Data Management\* and Confidentiality**

### Data Management:

All study parameters from the EMR will be downloaded by an EMR specialist via a report, de-identified, and housed in a Microsoft Excel database. Patient forms, including consent forms, will be stored in a locked file cabinet at Maple Tree Cancer Alliance. All patients will be assigned a Study ID number and a list linking patient names to Study ID number will be kept separately from the study data, on a password-protected computer. Data from patient forms will be entered into the master Microsoft Excel spreadsheet. Only Study ID will be used to identify patients in the spreadsheet.

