**Appendix A: Randomization Scheme using Block Size of 10**

Subject	Study Group Assignment
1	Control
2	Exercise
3	Exercise
4	Exercise
5	Control
6	Control
7	Control
8	Control
9	Exercise
10	Exercise
11	Exercise
12	Control
13	Control
14	Control
15	Exercise
16	Exercise
17	Control
18	Control
19	Exercise
20	Exercise
21	Control
22	Exercise
23	Exercise
24	Control
25	Exercise
26	Exercise
27	Control
28	Control
29	Exercise
30	Control
31	Exercise
32	Exercise
33	Control
34	Control
35	Exercise
36	Control
37	Control
38	Exercise
39	Exercise
40	Control
41	Exercise
42	Control

PROTOCOL TITLE: Randomized, Controlled Trial of an Individualized Exercise Oncology Program for Newly Diagnosed Breast Cancer Patients

43	Exercise
44	Exercise
45	Exercise
46	Control
47	Control
48	Exercise
49	Control
50	Control
51	Exercise
52	Exercise
53	Exercise
54	Control
55	Control
56	Control
57	Control
58	Exercise
59	Exercise
60	Control
61	Control
62	Control
63	Exercise
64	Exercise
65	Control
66	Exercise
67	Control
68	Exercise
69	Exercise
70	Control

PROTOCOL TITLE: Randomized, Controlled Trial of an Individualized Exercise Oncology Program for Newly Diagnosed Breast Cancer Patients

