**Appendix C: Master list linking patients to Study ID and documenting study participation for CONSORT reporting**

Patient Last Name	Patient First Name	Date Assessed for Eligibility (mm/dd/yyyy)	Excluded? (Y/N)	If Excluded, reason (did not meet eligibility criteria, declined to participate, other)	Study ID (N/A for those excluded)	Random Assignment (Exercise Group, Control Group)
					1	
					2	
					3	
					4	
					5	
					6	
					7	
					8	
					9	
					10	
					etc.

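### At least three of the twelve primary endpoints need an attribution of cause, and nothing in the plan keeps the person making it from knowing the group

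*Combined protocol and SAP*

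**What the plan says.** Section 4.0 lists twelve primary endpoints. Three carry a causal or relatedness condition in their definition:

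- a break in treatment, which requires at least 3 missed "fractions due to patient condition, determined via EMR";
- "Hospital readmission for the same presenting issue, as determined via EMR";
- "Cancer treatment-related side effects, determined via EMR".

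A fourth, "Medications for cancer treatment symptom management, determined via EMR", arguably needs a decision on what each drug was given for.

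On data handling, section 17.0 has an EMR specialist download the study parameters as a report, which is then de-identified and held in Excel. It adds that "Only Study ID will be used to identify patients in the spreadsheet". Section 19.0 says that identifiers are replaced by the Study ID. Section 17.0 also keeps the list linking names to Study IDs apart from the data, on a password-protected computer. Section 9.0 places abstraction after all patients have finished.

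On allocation, Appendix A ("Randomization Scheme using Block Size of 10") prints the group for subjects 1 to 70. Appendix C ("Master list linking patients to Study ID and documenting study participation for CONSORT reporting") has Study IDs pre-printed 1, 2, 3 and so on, issued only to patients who are not excluded, with the random assignment on the same row. Section 15.0 states that the "study will not be blinded; patients and treating physicians will be aware of group status".

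**The concern.** A report can supply dates and counts. Whether fractions were missed because of the patient's condition, whether a second admission is for the same problem, and whether a symptom is due to treatment are attributions that someone has to make. The plan does not say who makes them, by what rule, or whether that person is masked. By contrast, the lymphedema safety endpoint in section 4.0 does name a decider, the treating oncologist.

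If the person attributing cause knows the group, ambiguous events can be read in the expected direction without any intent. Breaks and readmissions are both part of hypothesis H1. Masking patients and physicians is not possible in this trial, but masking a retrospective classification is.

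**Working it through.** **Step 1. How many endpoints are exposed?** Three of twelve by their wording, or four if symptom-management medications are included. Total missed fractions, ER visits and length of stay are counts or dates and need little or no attribution. Total missed fractions is the endpoint that section 12.0 uses for sizing.

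**Step 2. Could the key reveal the group?** Appendix A has 70 entries, 35 Exercise and 35 Control, with 5 of each in every one of the 7 blocks of ten. This agrees with sections 6.0 and 12.0. Study IDs run 1, 2, 3 and so on, go only to enrolled patients, and no separate randomization number is described. If Study ID equals subject number, the ID gives the group for all 70 records to anyone holding the protocol. Storing the name list separately protects names but would not hide the group in that case. If the numbers differ, this route closes, but the plan still provides no masking.

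**Step 3. Where might the attribution be made?** The documents allow two workflows:

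| Who attributes cause | Knows the group? | Can later masking help? |
|---|---|---|
| A person classifying the extract after the trial | Not prevented | Yes |
| Treating staff, as charted during care | Physicians do (section 15.0) | No |

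**Step 4. What could this do to the break endpoint?** The documents give no break rates, so every rate here is assumed. Suppose 10% of each arm has a clear break due to patient condition, and a further 20% miss 3 or more fractions for an ambiguous reason.

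- Control, half of the ambiguous cases counted: 0.10 + 0.20 × 0.50 = 0.20, or 7 of 35.
- Exercise, a quarter counted: 0.10 + 0.20 × 0.25 = 0.15, or 5.25 of 35 on average.
- Exercise, none counted: 0.10 + 0.20 × 0 = 0.10, or 3.5 of 35 on average.

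The apparent difference is 5 or 10 percentage points with no true effect.

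**Step 5. What happens to the false-positive risk?** Use a two-sided test at 0.05 with n = 35 per arm. The chance of a significant result favouring exercise is about Φ[(pC − pE − 1.96 × SE0) / SE1], where SE0 = √[2p̄(1 − p̄)/35], p̄ is the mean of the two rates, and SE1 = √{[pC(1 − pC) + pE(1 − pE)]/35}. With no bias it is 2.5%.

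- 20% v 15%: SE0 = 0.0908, SE1 = 0.0906; (0.05 − 0.1780)/0.0906 = −1.41, giving about 7.9%.
- 20% v 10%: SE0 = 0.0854, SE1 = 0.0845; (0.10 − 0.1673)/0.0845 = −0.80, giving about 21%.

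A second set of assumptions takes a control rate of 10% to 30%, with 10% to 30% of exercise-arm breaks reclassified as not due to patient condition. The same formula gives about 3.5% (10% v 9%) to 13.5% (30% v 21%). Event counts are small, so all of these are rough.

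**The case against.** The strongest reply is that the documents describe no post-trial classifier at all. Cause may simply be read from the chart, in which case recoding IDs afterwards would change nothing. This stands, and it is why the any-reason break count belongs in the fix: it needs no attribution, whoever would have made it.

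It can also be said that the name list is stored separately and that no section equates Study ID with the Appendix A number. Both are correct. The master list is therefore not an open route to the group, and the Appendix A route rests on inference.

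A reader might infer that exercise-program staff will classify outcomes knowing the group. The documents do not support this. The provider's research intern has documented roles in consent and eligibility, and no section gives the intern or a trainer any part in classifying endpoints.

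Finally, the illustrated bias would not usually be significant by itself: 20% v 10% gives z = 0.10/0.0854 = 1.17, p about 0.24. This is true of the expected result. The bias would still distort the estimate and, as step 5 shows, raise the chance of a false positive.

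**Conclusion.** The gap is real but bounded. At least three of the twelve primary endpoints depend on an attribution for which the plan sets no decider, rule or masking, and nothing prevents the person making it from knowing the group. It would overstate the point to say that the Study ID does reveal the group, or that unmasked classification will occur. The first is a plausible inference from the numbering, and on the second the documents are silent.

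The size of any bias is unknown. The 20% v 15% and 20% v 10% figures, and the false-positive risks derived from them, illustrate assumed inputs and do not estimate what will happen in this trial. The endpoint used for sizing is little affected. The point concerns classification of outcomes, not concealment of allocation before enrolment. It should be settled before the EMR data are abstracted.

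**What to change.** In sections 4.0 and 17.0:

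1. Key the EMR extract used for classification to a random code unrelated to Appendix A, and leave the assignment out of it.
2. Have an existing team member who does not deliver the exercise program classify the cause-dependent endpoints by written rules, with references to the program removed where practicable.
3. Lock the classification before assignments are merged.
4. Report 3 or more missed fractions for any reason alongside the cause-dependent break. It comes from the missed-fraction count already collected, and it guards the break endpoint against attribution bias from either workflow. It does not protect readmissions or side effects.
5. Before writing the readmission rule, reconcile the 30-day readmission in sections 1.0 and 2.0 with the same-issue readmission in section 4.0, which gives no time window.

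The cost is protocol wording and a modest data-preparation step; item 4 is free. Sample size does not change. The documents do not describe the team beyond saying that resources are adequate (section 25.0), so a suitable classifier among existing staff is an assumption. Notes may still occasionally reveal the group, and causes charted by unblinded staff remain beyond repair by masking.

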## **16.0 Potential Benefits to Subjects\***

Participants in the exercise intervention may experience reduced pain and relief from other effects of cancer treatment, thus reducing breaks in treatment and hospital or ER visits. Participants may also experience improved energy and mood and may establish a positive behavioral pattern of physical activity that will extend beyond the study.

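### Length of stay appears to be tested only among patients who were hospitalised, a group formed after randomisation, so the comparison can be biased in either direction

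*Combined protocol and SAP*

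**What the plan says.** Section 4.0 (Primary Study Endpoints) includes "Hospital length of stay (if hospitalized), as determined via EMR". The qualifier in brackets is the only statement about which patients have a value.

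The Data Analysis Plan in Section 17.0 covers all continuous endpoints together: "Differences between study groups on continuous endpoints will be evaluated using independent samples" t-tests if they are normally distributed by Shapiro-Wilk, and Mann-Whitney U tests if they are not. It adds "Alpha will be set to .05, two-tailed for all tests". It does not mention length of stay, does not define an analysis set, and does not assign 0 days to a patient who is never admitted.

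The trial expects the intervention to change hospital use. H1 in Section 2.0 predicts "fewer hospital encounters, fewer 30-day hospital readmissions" in the exercise group, and Section 16.0 describes relief of treatment effects as "thus reducing breaks in treatment and hospital or ER visits". Section 3.0 says that earlier retrospective data showed that exercise "significantly reduced ED visits, 30-day readmissions, and length of hospital stays", and gives prospective analysis of cost savings as the purpose of this study.

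The nearest companion endpoint is "Inpatient and outpatient hospital encounters, as determined via EMR", which pools the two kinds of encounter. No listed endpoint is the proportion of patients admitted or the total number of days in hospital.

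**The concern.** Whether a patient is hospitalised is decided after randomisation and is something the intervention is meant to influence. If exercise works as H1 supposes, the hospitalised patients in the exercise arm are a different selection from those in the control arm. A difference in their mean stay may then reflect who was admitted and not how long a given patient stayed. The problem is greatest when the intervention is effective.

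Two consequences follow. First, a true reduction in hospital days could appear as a longer stay, or a difference in stay could appear although no admitted patient's stay was shortened. Second, the test rests on the few patients admitted within 12 weeks and not on 35 per arm. Because inpatient and outpatient encounters are pooled, the other endpoints would not readily show that a change in who was admitted lay behind the result.

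**Working it through.** The documents give no admission rate, no mean or SD of stay, and no design figure for length of stay; the power statement in Section 12.0 concerns missed fractions only. There is therefore no figure of the plan's own to reproduce. All rates and stays below are assumptions, chosen to show direction. The 35 per arm is from Section 12.0.

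**Exercise prevents short stays.** Assume that the control arm has six 2-day and three 6-day stays, one per patient, and that exercise prevents three of the short ones and changes nothing else.

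| | Control | Exercise |
|---|---|---|
| Total days | 6×2 + 3×6 = 30 | 3×2 + 3×6 = 24 |
| Mean stay, hospitalised only | 30/9 = 3.33 | 24/6 = 4.00 |
| Days per randomised patient | 30/35 = 0.86 | 24/35 = 0.69 |

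The restricted mean makes exercise look worse; the all-randomised mean shows fewer days. The assumed control admission rate is 9/35 = 26%.

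**A second model, run in both directions.** Assume that 10% of controls have a 2-day stay and 10% a 6-day stay. The control mean among the hospitalised is (0.10×2 + 0.10×6)/0.20 = 4.00, and days per randomised patient are 0.80.

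- Half of the short stays prevented: (0.05×2 + 0.10×6)/0.15 = 4.67 among the hospitalised; 0.70 per randomised patient. The restricted comparison points the wrong way.
- Half of the long stays prevented: (0.10×2 + 0.05×6)/0.15 = 3.33 among the hospitalised; 0.50 per randomised patient. The restricted comparison favours exercise, yet in this model no admitted patient's stay was shortened. The whole difference in mean stay comes from who was admitted.

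**Size of the subgroup.** At assumed admission rates of 10%, 20% and 30%, the restricted test has 35×0.1 = 3.5, 35×0.2 = 7 and 35×0.3 = 10.5 patients per arm. Two-sided t-test power for an assumed standardised difference of 0.5 is then about 8%, 14% and 19%.

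**What the tests would do.** The first illustration was simulated with 35 patients per arm, each having a 2-day stay with probability 6/35 (control) or 3/35 (exercise) and a 6-day stay with probability 3/35 in both arms.

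- Hospitalised-only Mann-Whitney: significant against exercise in about 7% of trials.
- Mann-Whitney on days in all randomised patients: significant in about 12%. The all-randomised mean still pointed the wrong way by chance in about 30%.
- With the control probabilities in both arms, so no true difference: a plain Poisson comparison of days was significant in about 27% of trials, and Mann-Whitney in about 5%. Days come in whole stays and are not independent events, so the Poisson variance is too small.

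**The case against.** The strongest reply is that the bracketed qualifier may only note when the EMR item exists, in a list of items to abstract. The analysis paragraph is generic and never says that patients without an admission are dropped. That is fair: a reader might infer that a hospitalised-only analysis is definitely planned, and the documents do not go that far. But nothing in them gives the other patients a value, so the restricted analysis is what results from following the text as it stands.

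A reader might also infer that the endpoint will make exercise look harmful. The documents do not support this. They do not say which admissions exercise would prevent, and if long ones are prevented the comparison favours exercise. Even when short ones are prevented, a significant false harm is uncommon (about 7% in the illustration). The usual result would be a misleading point estimate.

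Encounters and readmissions are also listed as primary endpoints without restriction to a subgroup, so length of stay would not be read alone. This helps only in part, because inpatient and outpatient encounters are pooled.

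Finally, length of stay is one of 12 listed primary endpoints and is absent from H1 and from the power statement. This stands, and it limits the consequence.

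**Conclusion.** The concern holds in this form: on the plain reading, a listed primary endpoint is compared between subgroups formed after randomisation, the trial expects the intervention to alter those subgroups, and the plan has no safeguard. The direction of the bias cannot be known in advance. The illustrated reversal (3.3 against 4.0 days among the hospitalised; 0.86 against 0.69 per randomised patient) depends on assumed stays and on short admissions being the ones prevented. It shows what can happen and does not forecast the result.

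It would be too strong to infer that the trial as a whole is undermined, since its stated hypotheses can be tested without this endpoint. It would also be too strong to infer that including all 70 patients makes hospital days an informative test: power was about 12% in the illustration. The gain is validity. The change is worth making because the stated purpose is cost savings, to which total days bear more directly than mean stay among those admitted. Its priority is at the lower end of recommended changes.

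**What to change.** In Section 4.0, define the endpoint as total hospital days over the 12 weeks per randomised patient, with 0 for a patient never hospitalised. The total also settles how repeat admissions are combined, which the present wording leaves open.

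In Section 17.0, name the analysis: compare this variable in all 70 patients by assigned group with the Mann-Whitney test already in the plan, or with a permutation test. Do not use a plain Poisson count model, because it ignores the clustering of days within stays. Report the proportion admitted in each arm, and give length of stay among the hospitalised as description without a test.

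The cost is an edit to two sections. The data come from the same EMR report, and Section 14.0 already provides for final non-physical-activity measures on withdrawn patients. The downside is a variable with many zeros and low power at 35 per arm, which the report should acknowledge.
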